7.1.3 List of Planned Listings

- 1. Study medication batch numbers
- 2. Randomisation scheme and codes (Randomised patients set)
- 3. Patient disposition I (Enrolled patients)
- 4. Patient disposition II (Randomised patients set)
- 5. Relevant protocol deviations (Full analysis set)
- 6. Analysis sets
- 7. Exclusions from analysis sets
- 8. Demographic Characteristics (Randomised patients)
- 9. Baseline characteristics (Randomised patients)
- 10. Medical and surgical history (Randomised patients set)
- 11. All current medications (Safety analysis set)
- 12. All concomitant medications (Safety analysis set)
- 13. Metformin treatment details (Safety analysis set)
- 14. Insulin Treatment details (Safety analysis set)
- 15. Study Drug Accountability (Safety analysis set)
- 16. Exposure Data (Safety analysis set)
- 17. Titration data (Safety analysis set)
- 18. Efficacy parameters over time (Full analysis set)
- 19. Efficacy parameters I (Full analysis set)
- 20. Efficacy parameters II (Full analysis set)
- 21. SF-36 raw data (Full analysis set)
- 22. SF-36 derived data (Full analysis set)
- 23. HFS-II Worry Scale (Full analysis set)
- 24. IWQOL-Lite raw data (Full analysis set)
- 25. IWQOL-Lite derived data (Full analysis set)
- 26. Adverse Events (Safety analysis set)
- 27. Serious adverse events (Safety analysis set)
- 28. Adverse Events leading to discontinuation of study medication (Safety analysis set)
- 29. Adverse Events of special interest (Safety analysis set)
- 30. Events of hypoglycaemia I (Safety analysis set)
- 31. Events of hypoglycaemia II (Safety analysis set)
- 32. Laboratory data (Safety analysis set)
- 33. Marked Laboratory Abnormalities data (Safety analysis set)
- 34. Liver Function Tests (Safety analysis set)
- 35. Vital Signs (Safety analysis set)
- 36. Abnormal ECG Findings (Safety analysis set)
- 37. Pregnancy Data (Safety analysis set)

7.2 Appendix II – Inclusion and Exclusion Criteria

Table 13. Patient inclusion and exclusion criteria

Inclusion criteria

- 1. Provision of informed consent prior to any study-specific procedures
- Is able to read, understand, and sign the Informed Consent Forms (ICFs) and, if applicable, an Authorisation to Use and Disclose Protected Health Information form, communicate with the Investigator, understand and comply with protocol requirements (including the use of diary and glucose meter measurements)
- 3. Is male or female of \geq 18 and \leq 75 years old at time of informed consent
- 4. Has a documented diagnosis of T2DM
- 5. Has a HbA1c of ≥7.5% and ≤10.5% based on central laboratory results from Visit 1, with individual need for therapy escalation
- 6. Currently treated with a stable MTD (≥1500 mg/day) of metformin therapy for at least 8 weeks prior to Enrolment visit
- 7. Has a BMI of \leq 45 kg/m² at enrolment visit
- 8. Has a C-peptide laboratory value of ≥1.0 ng/mL (0.33 nmol/L; 333.3 pmol/L) based on central laboratory results from Visit 1
- 9. For females only: women not of childbearing potential, or if they are women of childbearing potential (WOCBP), they must comply with the following:
 - Are not pregnant or breastfeeding
 - Have a negative urine pregnancy test result (minimum sensitivity 25 IU/L or equivalent units of human chorionic gonadotropin, beta subunit [βhCG]) at Visit 1 (Enrolment) and prior to randomisation.
 - Using or willing to adopt a highly effective method of birth control to avoid pregnancy throughout the study and for at least 4 weeks after the last dosing of study medication

Exclusion criteria

- Clinically diagnosed with Type I diabetes, known diagnosis of maturity onset diabetes of the young (MODY), or secondary diabetes mellitus or known presence of glutamate decarboxylase 65 (GAD65) antibodies
- 2. History of diabetic ketoacidosis, hyperosmolar nonketotic coma, or corticosteroid induced Type 2 diabetes
- 3. Symptoms of poorly controlled diabetes including, but not limited to, marked polyuria, polydipsia, and/or greater than 10% weight loss during the 3 months prior to Enrolment

- 4. FPG >270 mg/dL (>15 mmol/L) assessed based on central laboratory results from Visits 1
- 5. History of diabetes insipidus
- 6. Patients with clinically significant thyroid disease or uncontrolled thyroid disease needing initiation or adjustment of thyroid treatment per Investigator's judgement. Abnormal thyroid stimulating hormone (TSH) value at Enrolment will be further evaluated by free thyroxine (T4). Patients with abnormal free T4 values will be excluded
- 7. History of bariatric surgery or lap-band surgery, or either procedure is planned during the time period of the study. History of liposuction is allowed.
- 8. History of any unstable endocrine, psychiatric, rapidly progressing or unstable renal disease, or rheumatic disorder, as judged by the Investigator.
- Patients who, in the judgment of the Investigator, may be at risk for dehydration or volume depletion that may affect the patient's safety and/or the interpretation of efficacy or safety data
- 10. Has evidence of current abuse of drugs or alcohol or a history of abuse within the past 52 weeks that, in the Investigator's opinion, would cause the individual to be noncompliant
- 11. Clinically significant cardiovascular disease or procedure within 3 months prior to Enrolment (ie, MI, cardiac surgery, coronary artery bypass surgery, coronary stent placement, coronary angioplasty, unstable angina, stroke, transient ischaemic attack, or unstable or previously undiagnosed arrhythmia) or expected to require coronary revascularization procedure during the course of the study
- 12. Severe uncontrolled hypertension defined as systolic BP ≥180 mmHg and/or diastolic BP ≥110 mmHg at any visit up to and including Randomization (Visit 2)
- 13. Presence or history of severe congestive heart failure (New York Heart Association Class III and IV [CCNYHA 1994]), unstable or acute congestive heart failure, and/or known left ventricular ejection fraction of ≤40%
- 14. Creatinine clearance (CrCl) of <60 mL/min based on central laboratory results from Visit 1
- 15. Familial renal glucosuria. This condition is diagnosed as glucosuria (>1.0 mmol/L urine) in the presence of normoglycaemia in patients without the diagnosis of diabetes mellitus
- 16. Significant hepatic disease, including, but not limited to, severe hepatic insufficiency and/or significant abnormal liver function defined as aspartate aminotransferase (AST) and/or alanine aminotransferase (ALT) of >3x upper limit of normal (ULN) based on central laboratory results from Visit 1
- 17. Serum total bilirubin (TB) of >2 mg/dL (34.2 μ mol/L [patients with documented Gilbert's syndrome will be allowed to enrol]) based on central laboratory results from Visit 1
- 18. History of, or currently have, acute or chronic pancreatitis or have triglyceride concentrations ≥500 mg/dL based on central laboratory results from Visit 1.
- 19. History of severe hepatobiliary disease or hepatotoxicity with any medication
- 20. Positive serologic evidence of current infectious liver disease, including patients positive for

Hepatitis B viral antibody IgM, Hepatitis B surface antigen, and Hepatitis C virus antibody

- 21. History of malignancy within 5 years of Visit 1 (Enrolment), with the exception of treated in situ basal cell or squamous cell carcinoma of the skin
- 22. Haemoglobin <10 g/dL (<100 g/L) or 6.2 mmol/L for men; haemoglobin <9.0 g/dL (<90 g/L) or 5.9 mmol/L for women
- 23. History of chronic haemolytic anaemia or haemoglobinopathies (for example, sickle cell anaemia, thalassemia, sideroblastic anaemia). Mild haemolysis due to artificial heart valves or due to sickle cell trait is not an exclusion criterion except when haemoglobin levels are too low (as defined in haemoglobin criteria above)
- 24. Donation or transfusion of blood, plasma, or platelets within the past 12 weeks prior to Enrolment, or planning to donate blood during the study
- 25. Concomitant treatment with loop diuretics at Visit 2 (Randomisation/baseline.
- 26. Administration of any antihyperglycaemic therapy, other than metformin, during the 8 weeks prior to Visit 1 (Enrolment)
- 27. Administration of any other IP or participation in any interventional clinical studies 30 days prior to Visit 1 (Enrolment)
- 28. Treatment with systemic glucocorticoids equivalent to oral prednisolone ≥10 mg (betamethasone ≥1.2 mg, dexamethasone ≥1.5 mg, hydrocortisone ≥40 mg) per day for >7 days within 30 days prior to enrolment
- 29. Prescription or over-the-counter weight loss medications within 3 months prior to Visit 1 (Enrolment)
- 30. Has a clinically significant medical condition that could potentially affect study participation and compliance with the treatment and study procedures, or which may pose a significant risk to the patient and/or personal well-being, as judged by the Investigator
- 31. Has clinically significant abnormality identified on physical examination, ECG, or laboratory tests (clinical chemistry, haematology, and urinalysis) as judged by the Investigator at Visit 1 (Enrolment) would compromise the patient's safety or successful participation in the clinical study
- 32. Has known contraindications, allergies, or hypersensitivities to any study drug or excipient as outlined in the IBs or local package inserts for metformin, SU, saxagliptin, and dapagliflozin
- 33. Ongoing weight loss more than 5% over the last 3 months prior to Visit 1 (Enrolment)
- 34. Known immunocompromised status, including patients who underwent organ transplantation
- 35. Involvement in the planning and/or conduct of the study (applies to AstraZeneca staff and/or staff at the study site)
- 36. Previous screening, enrolment or randomisation in the present study

7.3 Appendix III – Laboratory Parameters and Marked Abnormalities

Table 14. Laboratory parameters

Haematology/Haemostasis (whole blood)	Clinical Chemistry (serum or plasma)
B-Red blood cell count	S/P-Creatinine
B-Leukocyte count	S/P-Bilirubin, total (TB)
B-Haemoglobin (Hb)	S/P-Alkaline phosphatase (ALP)
B-Haematocrit	S/P-Aspartate transaminase (AST)
B-Platelet count	S/P-Alanine transaminase (ALT)
	S/P-Uric acid
	S/P-Potassium
	S/P-Calcium, total
	S/P-Sodium
	S/P-Chloride
	S/P-Bicarbonate
	S/P-Magnesium
	S/P-Phosphorus

Table 15. Marked abnormality criteria for safety laboratory variables

		Marked abnormality criteria		
Clinical laboratory variables	Units	Low	High	
Haematology				
HCT males/females	0/0	< 20%	> 55%	
HCT males/females	0/0		> 60%	
Hemoglobin	g/L	< 60 g/L	> 180 g/L	
males/females				
Hemoglobin	g/L		> 200 g/L	
males/females				
Blood chemistry				
ALP	U/L		> 3X ULN	
ALT	U/L		> 3X ULN	
AST	U/L		> 3X ULN	
ALT	U/L		> 5X ULN	
AST	U/L		> 5X ULN	

		Marked	abnormality criteria
Clinical laboratory variables	Units	Low	High
ALT	U/L		> 10X ULN
AST	U/L		> 10X ULN
ALT	U/L		> 20X ULN
AST	U/L		> 20X ULN
Total Bilirubin	umol/L		$> 2X ULN \text{ if } PreRx \leq ULN;$
			> 3X ULN if PreRx > ULN
Glucose, Plasma	mmol/L	< 3 mmol/L	> 19.425 mmol/L
Unspecified			
Na (Sodium)	mmol/L	< 130 mmol/L	> 150 mmol/L
Na (Sodium)	mmol/L	< 120 mmol/L	
K (Potassium)	mmol/L	\leq 2.5 mmol/L	\geq 6.0 mmol/L
HCO3 (Bicarbonate)	mmol/L	_ ≤ 13 mmol/L	
Creatinine	umol/L		≥1.5X PreRx CREAT
Creatinine	umol/L		\geq 221 umol/L
Calcium	mmol/L	< 1.871 mmol/L	\geq 0.25 mmol/L from ULN and
			≥ 0.125 mmol/L from PreRx
			CA
Magnesium	mmol/L	< 0.5 mmol/L	> 2 mmol/L
PO4 (Phosphate)	mmol/L	Age 17-65: ≤	Age 17-65: ≥ 1.808 mmol/L
		0.581mmol/L	_
Magnesium		Age ≥ 66 : ≤ 0.678	Age \geq 66: \geq 1.647 mmol/L
_		mmol/L	
Urine			
UACR (Urinary	mg/g		> 1800 mg/g
Albumin-to-			
Creatinine Ratio)			

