4.9.7.1 Marked laboratory abnormalities

Laboratory abnormalities will be evaluated based on marked abnormality values (MA). The pre-defined criteria for marked abnormalities are detailed in Appendix III, Table 15. If both the baseline and on-treatment values of a parameter are beyond the same MA limit for the parameter, then the on-treatment value will be considered an MA only if it is more extreme (farther from the limit) than was the baseline value. If the baseline value is beyond the low MA limit, and the post-baseline value is beyond the high MA limit (or vice-versa), then the post-baseline value will be considered a MA.

Laboratory abnormalities during the double-blind treatment period will be summarised using all data regardless of use of rescue medication.

Additionally, patients with MA will be listed.

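### SAP Table 15 labels the age ≥66 phosphate limits as Magnesium; programmed as written, patients aged 66 to 75 would have no phosphate marked-abnormality criterion and an extra magnesium one

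*SAP*

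**What the plan says.** Three consecutive rows of Table 15 (SAP section 7.3, Appendix III) matter here.

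- Magnesium, mmol/L, no age split: low <0.5, high >2.
- PO4 (Phosphate), mmol/L, ages 17 to 65 only: low ≤0.581; the high limit reads "Age 17-65: ≥ 1.808 mmol/L".
- Magnesium again, units cell blank, age 66 and over: the low limit reads "Age ≥ 66 : ≤ 0.678" mmol/L and the high limit is ≥1.647 mmol/L.

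No row labelled phosphate covers age 66 and over. Section 4.9.7.1 makes the table operative ("Laboratory abnormalities will be evaluated based on marked abnormality values (MA") and takes the limits from Table 15. The outputs are planned table 97 and listing 33.

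Separately, exclusion criterion 22 (section 7.2, Appendix II, Table 13) sets "Haemoglobin <10 g/dL (<100 g/L) or 6.2 mmol/L for men" and "haemoglobin <9.0 g/dL (<90 g/L) or 5.9 mmol/L for women".

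**The concern.** A marked-abnormality limit is a decision threshold that should be fixed and correct before unblinding. Here the label and the content of one row disagree. A programmer who follows the label leaves older patients without a phosphate criterion and gives them a second, tighter magnesium criterion. A reader of table 97 would see a phosphate count and a magnesium count, with nothing to show that one age band was never assessed for phosphate. A programmer who recognises the slip would have to depart from the written plan without a documented basis.

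The affected band is populated: inclusion criterion 3 admits patients up to "75 years old at time of informed consent".

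The haemoglobin figures raise a different and smaller question. One criterion is stated in two units that give different limits for women, so eligibility could depend on the unit in which a site's result is read.

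**Working it through.** **Table 15: which analyte does the age ≥66 row belong to?**

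Inputs, all from Table 15: phosphate 17 to 65, 0.581 and 1.808 mmol/L; disputed row, 0.678 and 1.647 mmol/L; all-age magnesium, 0.5 and 2 mmol/L.

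1. Age bands. The phosphate row stops at 65 and the disputed row starts at 66. The first magnesium row has no age split, so an age-specific magnesium row would have no counterpart for younger patients.
2. Units. Every other repeated analyte in the table (ALT, AST, sodium, haemoglobin, creatinine) restates its unit on each row. The disputed row leaves the cell blank, as a continuation of the row above would.
3. Conversion to mg/dL (assumed atomic masses: P 30.974, Mg 24.305; mg/dL = mmol/L × mass / 10).
   - Phosphate 17 to 65: 0.581 × 3.0974 = 1.80; 1.808 × 3.0974 = 5.60.
   - Disputed row as phosphate: 0.678 × 3.0974 = 2.10; 1.647 × 3.0974 = 5.10.
   - Disputed row as magnesium: 0.678 × 2.4305 = 1.65; 1.647 × 2.4305 = 4.00.

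Read as phosphate, both limits come out at one decimal, as the 17 to 65 pair does. Read as magnesium, one limit is round and the other is not. The conversion is supporting evidence; the age bands carry the argument.

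**What changes if the row is programmed as labelled (age ≥66)?**

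| Value | All-age magnesium row | Age ≥66 row as labelled |
|---|---|---|
| Magnesium <0.5 or >2 | marked | marked |
| Magnesium 0.5 to 0.678 | not marked | marked |
| Magnesium 1.647 to 2 | not marked | marked |
| Phosphate, any value | no criterion | no criterion |

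The low magnesium threshold rises by 0.678 − 0.5 = 0.178 mmol/L, and the high threshold falls by 2 − 1.647 = 0.353 mmol/L.

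The SAP gives no age distribution. If 20% to 40% of the 930 planned patients were aged 66 or over (assumption), 0.20 × 930 = 186 to 0.40 × 930 = 372 patients would have no phosphate criterion.

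**Exclusion criterion 22**

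Inputs: men 10 g/dL or 6.2 mmol/L; women 9.0 g/dL or 5.9 mmol/L.

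1. Factor implied by the men's pair: 6.2 / 10 = 0.62 mmol/L per g/dL. Rounding of 6.2 allows 0.615 to 0.625.
2. Women, from g/dL: 9.0 × 0.62 = 5.58 mmol/L (5.54 to 5.63 over the rounding range), not 5.9.
3. Women, from mmol/L: 5.9 / 0.62 = 9.52 g/dL (9.44 to 9.59).
4. Most favourable rounding of both figures: 5.85 / 0.625 = 9.36 g/dL, still above 9.0.

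The gap is about 0.5 g/dL. A woman at 9.2 g/dL (9.2 × 0.62 = 5.70 mmol/L) passes on g/dL and fails on mmol/L.

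**The case against.** **The intended reading is easy to recover.** The blank units cell, the position under phosphate and the age bands all point to it, so a careful programmer may get it right. That stands, and it makes the consequence conditional. It does not make the written threshold correct.

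**Several rows per analyte are normal in Table 15.** ALT and AST have four each, and sodium has low limits of 130 and 120. A reader might infer that two magnesium rows giving different answers for the same value is itself a contradiction. It is not: sodium of 125 mmol/L is also marked on one row and not on the other. The defect is the label and the resulting absence of a phosphate row for age ≥66.

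**Older patients' phosphate is not lost to safety review.** Section 4.9.7 summarises laboratory values by visit for the whole Safety Analysis Set. Section 4.9.7.2 has a shift table of phosphorus to the highest category, and planned table 101 lists phosphorus for the minimum as well. None of these has an age limit, and all safety analyses are descriptive. This stands: only the flag in table 97 and listing 33 is at stake.

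**A false-alarm rate for magnesium.** A reader might assume a magnesium mean of 0.78 to 0.82 and SD of 0.07 to 0.08 mmol/L and infer that 2% to 10% of samples in older patients would be wrongly flagged. The SAP gives no such distribution. Section 4.9.7.1 also counts a value only if it is more extreme than a baseline already beyond the same limit, so a raw tail proportion is not a flag rate.

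**Haemoglobin.** A reader might infer that the wrong women are being excluded. The SAP does not show that: enrolment runs under the protocol, which is not at hand, and Appendix II only reproduces the criteria. Haemoglobin is not among the relevant protocol deviations in Table 5, and Table 15 uses its own haemoglobin limits in g/L.

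**Conclusion.** The Table 15 row for age ≥66 carries the wrong analyte label. Followed literally, it removes the phosphate marked-abnormality criterion for patients aged 66 to 75 and widens the magnesium criterion in the same patients by the two intervals shown. The identification rests on the document's own age bands and layout; the mg/dL conversion supports it under assumed atomic masses. The misflagging arises only if the label is programmed as written. The number of patients affected cannot be taken from the SAP; 186 to 372 is an illustration under an assumed age share. The primary and key secondary analyses, the analysis sets and the type I error control are untouched.

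The haemoglobin mismatch in exclusion criterion 22 is real and exceeds rounding, but it is an eligibility statement on which no analysis set or planned analysis depends. It is a minor point. Which of the two figures is intended cannot be decided from the SAP.

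**What to change.** In Table 15, change the label of the age ≥66 row to PO4 (Phosphate) and fill its units cell with mmol/L, so that magnesium keeps only its all-age row. Confirm that the programming specification for table 97 and listing 33 uses the corrected row, and record the correction before unblinding. In exclusion criterion 22, reconcile the women's g/dL and mmol/L figures with each other and with the protocol, and state which unit decides. The cost is two text corrections and one specification check; no new data or analyses are needed.

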7.4 Appendix IV – Missing data pattern for HbA1c

Table 16. Assessment of missing data patterns by visit and treatment group (Full analysis set)

Visit	Change from Baseline in HbA1c Assessments	DAPA + MET $(N = XXX)$	DAPA + SAXA + MET $(N = XXX)$	GLIM + MET $(N = XXX)$
Week X	Available at Week X	XXX (XX.X%)	XXX (XX.X%)	XXX (XX.X%)
	No baseline assessment available	X (X.X%)	X (X.X%)	X (X.X%)
	Missed Visit	X (X.X%)	X (X.X%)	X (X.X%)
	Lost to Follow-up	X (X.X%)	X (X.X%)	X (X.X%)
	Discontinued Study Medication	X (X.X%)	X (X.X%)	X (X.X%)
	Rescued	X (X.X%)	X (X.X%)	X(X.X%)
	Cumulative Patients Excluded:			
	Primary Efficacy Analysis	X (X.X%)	X (X.X%)	X (X.X%)
	Sensitivity Analysis*	X (X.X%)	X (X.X%)	X(X.X%)
Week Y	Available at Week Y	XXX (XX.X%)	XXX (XX.X%)	XXX (XX.X%)
	No baseline assessment available	X (X.X%)	X (X.X%)	X (X.X%)
	Missed Visit	X (X.X%)	X (X.X%)	X (X.X%)
	Lost to Follow-up	X (X.X%)	X (X.X%)	X (X.X%)
	Discontinued Study Medication	X (X.X%)	X (X.X%)	X (X.X%)
	Rescued	X (X.X%)	X (X.X%)	X(X.X%)
	Cumulative Patients Excluded:			
	Primary Efficacy Analysis	X (X.X%)	X (X.X%)	X (X.X%)
	Sensitivity Analysis*	X (X.X%)	X (X.X%)	X (X.X%)

Missed Visit = Patient has an HbA1c at a visit before and an HbA1c at a visit after the Missed Visit.

Lost to Follow-up (e.g., Right Censored) = Patient has an HbA1c at a visit before but no HbA1c assessments after the visit.

Discontinued Study Medication = Patient has discontinued study medication prior to that visit (will result in exclusion from Primary Efficacy analysis; may or may not have an HbA1c available).

Rescued = Patient has received rescue medication prior to that visit (will result in exclusion from Primary Efficacy analysis; may or may not have an HbA1c available).

Cumulative number (%) patients excluded from the primary efficacy analysis is the distinct patients within (LTFU + Discontinued Study Med + Rescued + No baseline available)

Cumulative number (%) patients excluded from the sensitivity analysis is the distinct patients within (LTFU + No baseline available)

^{*} Sensitivity analysis re-running MMRM including all values regardless of use of rescue medication or treatment discontinuation

7.5 Appendix V – IWQOL-Lite Scoring

The IWQOL-Lite is a 31-item self-reported assessment of quality of life in overweight or obese individuals. It scores on 5 dimensions: physical function (11 items); self-esteem (7 items); sexual life (4 items); public distress (5 items); and work (4 items). Raw scores for each scale will be computed for each of the five scales only if a minimum of 50% of the items for that scale are answered, and for the total score only if 75% of the answers for all items are completed. (The required number of minimum responses is: Physical Function=6 of 11; Self-Esteem =4 of 7; Sexual Life=2 of 4; Public Distress=3 of 5; Work=2 of 4; Total=24 of 31.) In computing raw scores, a pro-rated system for handling missing data will be used. To calculate the raw score for any scale or total score, the procedures are as follows:

1. Determine if the minimum number of items are answered for that scale. The required number of minimum responses is: Physical Function=6 of 11; Self- Esteem =4 of 7; Sexual Life=2 of 4; Public Distress=3 of 5; Work=2 of 4; Total=24 of 31.

Example 1: If an individual answered 5 of 11 Physical Function questions, the Physical Function score would be considered missing and coded as 999.

Example 2: If an individual answered 26 items on the entire scale, a valid score would be calculated for the IWQOL-Lite total.

2. Take the average of the valid items for that scale. Compute the average for the valid responses to items for that scale where 1="Never True" and 5="Always True". The average must be a number between 1 and 5. For example, if the respondent answered "3" on every item of the Physical Function scale, the mean would be 3.

Example 3: An individual answered the 11 Physical Function questions as follows (9 indicates missing question): 2, 3, 2, 4, 9, 2, 2, 3, 4, 9, 5. The individual answered 9 of 11 questions, with an average of 3.0 (27/9).

Example 4: An individual answered the 5 Public Distress questions as follows: 3, 1, 3, 4, 3. The individual answered 5 of 5 questions with an average of 2.8 (14/5).

3. Multiply that average by the total number of items for that scale. The total number of items on IWQOL-Lite scales are as follows: Physical Function=11, Self-Esteem=7, Sexual Life=4, Public Distress=5, Work=4, Total=31). Round to the nearest whole integer. For example, if the mean of the Physical Function scale is 3.0, then you would multiply 3.0 X 11 = 33.

Example 5: From the Physical Function answers in Example 3, multiply the average (3.0) times the number of total questions in the Physical Function scale (11) and round to the nearest whole integer: $3 \times 11 = 33$ (no need to round). This is the Physical Function Raw Score.

Example 6: From the Public Distress answers in Example 4, multiply the average (2.8) times the number of total questions in the Public Distress scale (5) and round to the nearest whole integer: $2.8 \times 5 = 14$ (no need to round). This is the Public Distress Raw Score.

In order to convert the IWQOL-Lite raw scores to the more familiar 0 (worst) to 100 (best) scoring using the following formulae:

- 1. Subtract the raw score (as calculated above) from the maximum score for each scale (Physical Function=55, Self-Esteem=35, Sexual Life=20, Public Distress=25, Work=20, Total=155).
- 2. Divide that difference by the range for each scale (Physical Function=44, Self-Esteem=28, Sexual Life=16, Public Distress=20, Work=16, Total=124).
- 3. Multiply that total by 100.

Example 7: From the Physical Function answers in Example 5, subtract the raw score (33) from the maximum score for Physical Function (55) and divide that result by the range for Physical Function (44) and multiply the result by $100: (55 - 33)/44 = .50 \times 100 = 50$.

Example 8: From the Public Distress answers in Example 6, subtract the raw score (14) from the maximum score for Public Distress (25) and divide that result by the range for Public Distress (20) and multiply by 100: $(25 - 14)/20 = .55 \times 100 = 55$.

An easy way to check the scoring is to enter a record with all 1's and a second record with all 5's. The first record should have all transformed scores equal to 100 and the second record should have all transformed scores equal to 0.
